16.3. Subject Information and Consent

Prior to completing any procedures or collecting any data that are not part of usual care, written informed consent will be obtained from the parent/guardian. For patients who are considered potentially eligible for the study based on case history, the study protocol will be discussed with the parent/guardian by a study investigator and clinic coordinator. The parent/guardian will be

given the Informed Consent Form to read. The parent/guardian will be encouraged to discuss the study with family members and their personal physician(s) before deciding whether to participate in the study. If the parent/guardian agrees to have the child participate, the Informed Consent Form will be signed. A copy of the consent form will be provided to the parent/guardian and another copy will be added to the participant's chart or retained by the center research staff. The signed informed consent document must be available for verification by the study monitors at all times.

All parties will ensure protection of subject personal data and will not include subject names on any sponsor forms, reports, publications, or in any other disclosures. Subject names, address, date of birth and other identifiable data will be replaced by a numerical code consisting of a numbering system provided by Xeris Pharmaceuticals to de-identify the study subject. In the case of data transfer, Xeris Pharmaceuticals will maintain confidentiality and protection of subject personal data.

The informed consent document used in this study, and any changes made during the course of the study, must be prospectively approved by both the IRB and Xeris Pharmaceuticals before use.

16.4. Subject Recruitment

All types of subject recruitment or advertising information must be submitted to Xeris Pharmaceuticals or its designee and to the IRB for review and approval prior to implementation. Advertisements approved by the IRB may be used as recruitment tools.

16.5. Reporting of Safety Issues and Serious Breaches of the Protocol

In the event of any prohibition or restriction imposed (i.e., clinical hold), or if the investigator is aware of any new information which might influence the evaluation of the benefits and risks of the investigational product, Xeris Pharmaceuticals should be notified immediately. In addition, the investigator will inform Xeris Pharmaceuticals immediately of any urgent safety measures taken by the investigator to protect study subjects against any immediate hazard, and of any serious breaches of this protocol.

17. DEFINITION OF END OF TRIAL

LSLV is defined as the date the investigator reviews the last subject's final safety data and determines that no further evaluation is required for the subject to complete the trial.

18. PROCEDURES FOR MODIFYING THE PROTOCOL OR TERMINATING THE STUDY

18.1. Protocol Modifications and Deviations

The principal investigator and the sponsor's representative must sign this protocol and its amendments (if any) before initiating the study. The investigator will make all reasonable efforts to comply with the written protocol. Protocol modifications to ongoing studies that affect the safety of subjects or that alter the scope of the investigation, the scientific quality of the study, the experimental design, dosing, study assessments, the number of subjects exposed to test drug, or subject selection criteria must be made only after consultation between Xeris Pharmaceuticals and the investigator. All protocol modifications must be reviewed and approved by the IRB before the revised protocol can be implemented. Emergency revisions that eliminate an apparent hazard to subjects do not require preapproval by the IRB. However, the IRB must be notified in writing as soon as possible after the modification has been made. A copy of this communication must be forwarded to Xeris Pharmaceuticals. All departures from the protocol must be fully documented in the source documents and the CRFs of the subjects involved.

18.2. Study Termination

The study may be prematurely terminated at any time because of a regulatory authority decision, change in opinion of the IRB, safety problems, or at the discretion of Xeris Pharmaceuticals or the principal investigator. Circumstances that may warrant premature study termination at a one or more clinic sites or overall include, but are not limited, to the following:

- Determination of unexpected, significant, or unacceptable risk to subjects
- Failure to enter subjects at an acceptable rate
- Insufficient adherence to the requirements of the protocol
- Insufficient provision of complete and evaluable data
- Plans to modify, suspend, or discontinue development of the study drug

If the study is prematurely terminated or discontinued, Xeris Pharmaceuticals will promptly notify the investigator documenting the reason for study termination, and specific procedures for termination will be arranged by the sponsor in coordination with the investigator. After notification, the investigator must remove all participating subjects from ongoing study treatment within 7 days. All study materials must be collected and all CRFs completed to the greatest extent possible, and all study materials must be returned to Xeris Pharmaceuticals or its designee in a timely manner.

19. PUBLICATION OF STUDY RESULTS

Publication of study results is discussed in the Clinical Study Agreement.

21. APPENDICES

APPENDIX 1. DRAIZE SCALE

- Draize Scale for Erythema and Edema: to be used for physical examination abnormalities at the infusion site.
- Investigative Site Instructions: The infusion site should be examined after removal of the OmniPod® pump and recorded on the case report form.
- For any infusion site with an Erythema or Edema Formation score > 0, follow-up examinations should be performed until scores equal 0.

Erythema Formation		Edema Formation	
Description	Score	Description	Score
No erythema	0	No edema	0
Very slight erythema Barely perceptible	1	Very slight edema Barely perceptible	1
Well defined erythema	2	Well defined edema	2
Moderate erythema	3	Moderate edema Raised approx. 1 mm	3
Severe erythema Beet redness to slight eschar formation	4	Severe edema Raised more than 1 mm and beyond exposure area	4

APPENDIX 2. OMNIPOD® WEIGHING PROCEDURES

The following procedures will be followed to load and weigh the OmniPod® pump.

1. Remove pod from original sealed plastic cover and set cover aside.
2. Load pod as per protocol:
 - a. If placebo group, load with 1 mL vehicle, using the kitted needle and syringe
 - b. If active group, load with 1 mL glucagon, using a 1 mL Injekt-F syringe and kitted needle
3. Using PDM, prime pod.
 - a. A small amount of fluid may collect under/around the needle shield; blot and discard.
4. Place pod back into the original opened plastic cover and place in Ziploc baggie labeled with the subject's study ID number.
 - a. Add a fresh sterile gauze pad to the baggie.
5. Weigh baggie and record weight to nearest whole mg.
6. Take PDM and baggie containing pod with original opened plastic cover and dry gauze pad to NICU.
7. Remove the needle shield and blot any pooled liquid using the gauze pad.
8. Place pod on patient as per protocol.
9. Place adhesive backing, needle shield, used gauze pad and original opened plastic cover back into the baggie and return it to Pharmacy.
10. When it is time to remove pod, retrieve plastic baggie from Pharmacy.
11. Deactivate and remove pod and place in plastic baggie and return baggie to Pharmacy with PDM.
12. Pharmacy will weigh plastic baggie, containing used pod, needle shield, adhesive backing and used gauze pad, and record weight to nearest whole mg.
13. Pharmacy will record reading from PDM regarding the amount of drug infused since priming.

Note: Per the manufacturer, the maximum allowable time between Pod priming and activation is 1 hour.

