9.2. Blinding

Blinding will be achieved through the availability of an indistinguishable placebo.

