9.3. Drug Supplies

9.3.1. Drug Product Formulation and Packaging

CSI-Glucagon™ is a room temperature stable, non-aqueous, injectable liquid formulation of glucagon. The formulation consists of 5 mg/mL synthetic glucagon peptide dissolved in a primary DMSO solvent, with trehalose added as stabilizing excipients. A volume of 1 mL of formulation is filled into West Pharmaceutical's 2 mL Crystal Zenith® pre-filled cyclic olefin polymer (plastic) vial with Flurotec® coated stopper. The drug product is stored at controlled room temperature (20-25°C) prior to use.

The placebo comparator to be used in this study is the vehicle for CSI-Glucagon™. It contains no glucagon, but otherwise has the same composition and is indistinguishable in appearance from the test product.

The CSI-Glucagon™ and matching placebo are packaged, labeled and distributed for Xeris under cGMP by MRI Global (Kansas City, MO).

For use during blinded Period 2, sites will be provided with a supply of active and placebo product packaged in identical vials with the same blinded label on each. A separate set of unblinded vials of active product will be supplied for use during open-label Period 3.

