9.3.3. Preparation, Dispensing and Administration

- CSI-Glucagon™ and vehicle will be supplied as 1 mL of non-aqueous solution in plastic Crystal Zenith (CZ) 2 mL vials. Each vial of CSI-Glucagon™ will be used to fill a single OmniPod® pump.
- CSI-Glucagon™ will be transferred to the OmniPod® using the kitted syringe and needle. Alternatively, a DMSO-compatible B Braun Injekt F® Low Waste Syringe 1 mL (supplied by Xeris) may be used along with the fill needle supplied by the pump manufacturer. If CSI Glucagon™ is not transferred into the OmniPod® within one hour of being drawn up into the syringe, the syringe, needle and drug should be discarded, and a fresh vial, needle and syringe should be used to fill the pod.

To maintain blinding during the randomized portion of the trial (Period 2), study medications will be blinded. The investigator will have the ability to unblind should such be necessary for the care of the subject in an emergency situation. During the open-label portion of the study (Period 3), study drug may be dispensed by any appropriately trained member of the study staff. During Period 3, dosing will be adjusted every 7 days as applicable based on the current body weight of the subject. During either period, the OmniPod® pump may be loaded with study drug by the pharmacist or other appropriately trained study staff.

The OmniPod® pump placement and study procedures will be performed by qualified/trained site staff who have read the OmniPod® Instructions for Use and following Table 3 for conversion of required glucagon flow rate to OmniPod® basal settings for pumping insulin.

Table 3: OmniPod® Controller Settings

Treatment	Desired Basal Rate	OmniPod® Setting	OmniPod® Setting (4 kg infant)
CSI-Glucagon™	2.5 µg/kg/hr	Infant weight in kg * 0.05 U/hr	0.2 U/hr
	5 µg/kg/hr	Infant weight in kg * 0.1 U/hr	0.4 U/hr
	10 µg/kg/hr	Infant weight in kg * 0.2 U/hr	0.8 U/hr
	15 µg/kg/hr	Infant weight in kg * 0.3 U/hr	1.2 U/hr
	20 µg/kg/hr	Infant weight in kg * 0.4 U/hr	1.6 U/hr

During Period 2 (blinded treatment), each OmniPod® will be used for a maximum of 48 hours. During period 3 (open-label), each OmniPod® will be used for up to 3 days, and will then be exchanged for a fresh pump. Before placement and after use each, each OmniPod will be weighed to the nearest whole mg (see Appendix 2).

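### Appendix 2 sets the pod-loading syringe by treatment arm: a blinded loader cannot follow it, and no unblinded loader is provided for

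*Combined protocol and SAP*

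**What the plan says.** Appendix 2 (OmniPod Weighing Procedures) opens by saying that it governs both loading and weighing. Step 2 then splits by arm:

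- Placebo (2a): "If placebo group, load with 1 mL vehicle, using the kitted needle and syringe".
- Active (2b): "If active group, load with 1 mL glucagon, using a 1 mL Injekt-F syringe and kitted needle".

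Elsewhere the plan says the following.

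- **9.2 Blinding**, in full: "Blinding will be achieved through the availability of an indistinguishable placebo".
- **9.3.1**, on Period 2 supply: "sites will be provided with a supply of active and placebo product packaged in identical vials with the same blinded label on each". On the placebo: "It contains no glucagon, but otherwise has the same composition and is indistinguishable in appearance from the test product".
- **9.3.3**: CSI-Glucagon "will be transferred to the OmniPod® using the kitted syringe and needle", with the 1 mL Injekt F as an optional alternative. No syringe is set for vehicle. In either period the pod may be loaded by the pharmacist or by other trained staff.
- **Synopsis, Period 2, Day 0**: a treatment dispenser loads the pump according to the randomization and hands it to study staff. The syringe is referred to 9.3.3.
- **10.2.2, Day 0, step 4**: the same loading step with the same reference to 9.3.3, but without the dispenser or the hand-over.
- **13.4 Interim Analysis**: the statistician who runs it is the only role that the documents call unblinded.

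**The concern.** A procedure that differs by arm belongs in a double-blind trial only if the person carrying it out is designated as unblinded and kept away from decisions that feed the endpoint. Here the procedure differs by arm and the designation is missing.

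The primary endpoint makes this matter. Section 5.1 defines treatment failure by the percentage reduction in GIR at 24 and 48 hours, and GIR is set at the bedside. Section 10.2.1 lets the investigator make more frequent or smaller GIR changes than the stated steps. Step 9 of 10.2.2 tells staff to adjust IV fluids as in Period 1, which reads as carrying that discretion into the blinded period. Staff who adjust GIR and also load the pod, or see which syringe was used, could learn the arm.

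**Working it through.** No power or alpha figure in the plan is at issue. The check is a comparison of passages, followed by two small calculations.

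**1. Can a blinded loader carry out step 2?** Only Period 2 has a placebo group, so the choice between 2a and 2b arises only there. Under 9.3.1 the Period 2 vials and labels are the same for both products. The vial therefore does not show which branch applies, and a loader working from it alone cannot comply.

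**2. Can anyone carry it out?** Yes, a loader who works from the allocation. The synopsis and 10.2.2 step 4 both speak of loading according to the randomization. That loader knows the arm. If vials were coded so that the loader stayed blind, step 2 could not be executed.

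**3. Does step 2 agree with 9.3.3?** No.

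| | Active | Placebo |
|---|---|---|
| 9.3.3 | Kitted syringe first, Injekt F optional | Not specified |
| Appendix 2, step 2 | Injekt-F | Kitted syringe |

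If kitted means the same item in both places, the 9.3.3 first choice for active is the syringe that Appendix 2 gives to placebo. The needles differ too: 9.3.3 pairs the Injekt F with the pump manufacturer's fill needle, and Appendix 2 pairs it with the kitted needle.

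**4. Is there a formulation reason for the split?** None is given. Section 9.3.3 describes the Injekt F as compatible with DMSO, but the placebo is the same vehicle without glucagon, so compatibility with DMSO would apply to both arms.

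**5. Is the loader separated from GIR decisions?** Partly.

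- For separation: the synopsis hand-over; the pod's movement between Pharmacy and ward; and step 6, "Take PDM and baggie containing pod with original opened plastic cover and dry gauze pad to NICU", which does not list the syringe. The statement that "study drug may be dispensed by any appropriately trained member of the study staff" is also confined to Period 3.
- Against: 9.3.3 lets other trained staff load in either period, and 10.2.2 step 4 drops the dispenser. Step 5 of 10.2.2 has the staff who apply the pump weigh it under Appendix 2, whose steps 1 to 5 run from loading to weighing with no change of actor.
- Nothing states that the loader is unblinded or has no part in adjusting GIR.

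**6. How many loadings?** Loadings = infants × pods per infant. Assume 1 pod, or 2 if the 12-hour replacement in 10.2.2 applies, with Appendix 2 followed at every site.

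| Stage | Infants | Loadings |
|---|---|---|
| Interim, 6 per arm | 12 | 12 × 1 to 12 × 2 = 12–24 |
| Final, 9 per arm | 18 | 18 × 1 to 18 × 2 = 18–36 |
| Final, 12 per arm | 24 | 24 × 1 to 24 × 2 = 24–48 |

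Replaced infants (9.1) and pod changes after an alarm or suspected occlusion (10.2.2) would add to these. They count occasions on which step 2 would apply, not instances of unblinding.

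**7. How sensitive is the interim decision to one infant?** The stopping limit in 13.2.1 is a one-tailed Fisher p of at most 0.0124. Take 6 of 6 placebo failures.

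- With 2 of 6 active failures (8 failures in 12): p = C(6,2) × C(6,6) / C(12,8) = 15/495 = 0.030. The trial continues with 3 more per arm.
- With 1 of 6 active failures (7 failures in 12): p = C(6,1) × C(6,6) / C(12,7) = 6/792 = 0.0076. The trial stops for efficacy.

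In this example one infant's classification changes the decision. This shows sensitivity; it does not estimate bias.

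**The case against.** The strongest reply is that Appendix 2 is a weighing appendix that was not kept in line with the body. Both loading steps, in the synopsis and in 10.2.2, send the reader to 9.3.3 for the syringe. The body cites Appendix 2 only for weighing, and step 2 itself defers to the protocol for loading. A site following 9.3.3 could load both arms alike. Further, 7.1 describes GIR as driven by a fixed algorithm applied equally to both groups, and 10.2.1 gives set changes by glucose band, so discretion is limited. Section 9.3.3 says that Period 2 medication will be blinded, and the pod's return to Pharmacy suggests that it was prepared there. Finally, 9.2 concerns the product, so a syringe seen only by the loader does not contradict it.

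Much of this stands as context. An unaligned appendix is a likely origin, and the hand-over and algorithm lower the risk. Carrying the GIR discretion into Period 2 is an inference from step 9 of 10.2.2, though a natural one. The kit is not defined, so it is not certain that kitted means the same item in both sections. Sites that cannot weigh pods are exempt from weighing under 9.3.4, so the number actually loaded under step 2 is unknown.

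It does not remove the conflict. Appendix 2 says that it will be followed for loading as well as weighing, trained staff other than the pharmacist may load in Period 2, and no section designates an unblinded loader.

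**Conclusion.** The concern holds. As written, step 2 cannot be followed by a blinded loader, reveals the arm to a loader who can follow it, and conflicts with 9.3.3. No text assigns Period 2 loading to an unblinded person with no role in GIR adjustment. That conclusion rests on the wording alone and is firm.

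The consequence is less certain. Exposure requires the same person to load and to adjust GIR, or someone adjusting GIR to see the syringe; the documents permit this but do not direct it. The loading counts rest on the assumptions stated with them. How often the arm would leak, and the effect on bias, type 1 error or power, cannot be derived from the documents. It should be fixed because it is a stated rule at odds with the blind, in a small trial whose primary endpoint is set at the bedside.

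**What to change.** Replace steps 2a and 2b of Appendix 2 with one Period 2 instruction: load 1 mL of the assigned blinded study drug, with the same syringe and needle type in both arms. The sponsor chooses the syringe from the two in 9.3.3. Amend 9.3.3 so that it names that choice, covers vehicle as well as CSI-Glucagon, and applies to replacement pods. The cost is text edits in two places, and possibly a supply adjustment so that one syringe type serves both arms; kit contents and stock are not given in the documents.

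If different syringes are truly needed, state the reason. State also that Period 2 loading is done by a dispenser or pharmacist who is unblinded and has no role in GIR adjustment or endpoint assessment. Then reconcile the synopsis loading step, 9.3.1, 9.3.3, 10.2.2 and Appendix 2. That route costs more, because each of the approximately 6 sites would need a designated unblinded loader.

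Neither route changes the sample size, power or alpha.
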